- The number of days before the first alcohol intake (at least one standard glass) according to the patient's own information.
- The number of days before the first heavy drinking day according to the patient's own information.

Clinical Global Impression improvements after 6 and 12 months, respectively

The patients who after 12 months are "significantly improved" or "greatly improved", ie they receive a value of 1 or 2 on the CGI-I scale (see section 8.3.6) are considered to have responded to the treatment (responders). Patients with a value of 3 or higher are classified as non-responders. The proportion of responders will be compared between the treatment arms.

Change in quality of life measured with EQ-5D

EQ-5D is an accepted and widely used measure of quality of life, and the form is recommended by TLV (Dental and Pharmaceutical Benefits Agency). A general quality of life measure such as EQ-5D provides an overall picture of the study participants' perceived health, and is a good basis for health economic analyzes.

AUDIT improvement

The National Board of Health and Welfare prioritises AUDIT as a tool for identifying alcohol problems. The treatment arms will be compared with respect to:

- Proportion of patients who after 12 months have lowered their AUDIT score
- Proportion of patients who after 12 months have lowered their AUDIT score to at least one zone
- Proportion of patients who after 12 months have a risk level <II
(i.e. less than 6 AUDIT points for women, 8 AUDIT points for men).

SADD improvement

Change in alcohol dependence measured as the difference in SADD scores at 12 and 6 months, respectively, compared with baseline).

Compliance with agreed treatment

The patient remains in treatment

At each study-related visit, it is documented whether the patient remains in treatment or has interrupted his or her treatment. The proportion of patients who remain in treatment will be compared between the patient groups over time.

Compliance with TripleA

For the TripleA arm, the proportion of measurements performed compared to announced measurements will be reported. The information is retrieved from the TripleA database where all notifications and measurements are logged. Corresponding information is not available for the control arm for obvious reasons.

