7.3.13. Safety reporting

Patients in the TripleA arm should be asked at each visit if there have been any incidents related to the use of TripleA.

Alcohol-related hospitalization since the previous visit must be noted in CRF for all study participants.

Time: Made at each visit.

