7.5. Loss

7.5.1. Loss of patients

The reason why a patient discontinues treatment or study must be documented and these patients must be followed up. Patients who discontinue the study will not be reimbursed. The loss will be reported.

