9.1. Statistical design, method and analysis procedure

9.1.1. General

Continuous data will be summarized using descriptive statistics where the following parameters will be reported: number of observations, number of missing observations, mean, standard deviation, median, minimum and maximum. Categorical data will be presented with number (n) and percentage (%).

In addition to evaluation of all study data from the entire study period (12 months), 6-month data will also be evaluated.

Factors such as gender, severity of addiction, motivation, form of therapy and socio-economic factors will be considered as covariates in the statistical analyzes.

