9.2. Sample size, significance level and statistical strength

The primary endpoint is the proportion of patients who do not have heavy drinking days during a 4-week period after 12 months from baseline. Assuming that the proportion is 30% in the control group and you want to be able to detect a difference of 30% between the TripleA and the control group, 42 patients are needed per treatment group to achieve a strength of 80% with a double-sided test of 5% significance level. Assuming that the proportion of patients who do not complete the study is about 20%, a total of 106 patients need to be randomized, ie 53 per group.

Expected loss

The drop-out rate in alcohol studies is usually quite large.

At inclusion, the patient is asked to provide at least one contact person that the study staff can contact if the patient is absent from agreed meetings, interrupts treatment and / or stops blowing. Patients who do not wish to continue their treatment should be informed that they are welcome to continue using TripleA and / or alcohol, or otherwise report their alcohol consumption, as this is valuable information for the study. If the patient wants to stop the study completely, the study staff should at least ask the question "how many standard glasses have you drunk the most in one day since we were last seen?". This gives the opportunity to assess whether there has been a heavy drinking day or not.

A certain loss of patients during the course of the study is expected. Three types of missing data can be identified.

1. Patients who choose to discontinue treatment and study participation.
2. Patients who choose to discontinue treatment but who continue to provide information on alcohol intake (i.e. remain in the study)

Patients who continue treatment but who do not provide complete information on alcohol intake.

4. Patients who miss occasional visits.

All efficacy evaluations will be performed on two analysis populations, a population consisting of all randomized patients contributing efficacy data from at least one baseline visit (ITT) and a population consisting of all patients who completed the study according to the protocol (PP).

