In the first population, missing values will be handled primarily according to the principle of multiple imputation (MI). In this approach, the missing values according to type 1 in the list above will be directly imputed according to the MI principle while values of type 2 in the list above, i.e. which are collected after treatment interruption, will remain as missing values, which are then imputed. Missing values of type 3 in the list above, ie. incompletely completed alcohol intake data, are replaced according to the principles described for each variable in section 8.3, ie. in these situations there is data and thus MI does not need to be used. For missing values of type 4 in the list above, MI is used.

In addition to the MI approach, any exploratory analyzes will be made where the principle of last-observation-carried-forward (LOCF) can be used, as well as an analysis where only observed values are included in the evaluation.

In addition to the above, a separate evaluation will be made for patients according to type 2 in the list above where collected values after treatment interruption are used. When tabulating alcohol intake data from visit 1 to visit 6, this group will be reported on three lines where line 1 indicates the number of patients in this group who remain on the treatment at each visit, while line 2 indicates the number of patients in this group who discontinued treatment from each visit. The third row then constitutes the sum of row 1 and row 2, i.e. the whole group of patients in the active group who discontinued treatment at some point after visit 1 but still remained in the study.

The analyzes performed on the ITT population will be considered as the primary ones.

The safety assessment will be based on the ITT population.

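### Patients who leave the study are not asked about alcohol-related admissions, so a plain n (%) on the ITT set would modestly understate 12-month admissions: ask at exit and show observed follow-up by arm

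*Combined protocol and SAP*

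**What the plan says.** - **Capture.** Section 7.3.13: "Alcohol-related hospitalization since the previous visit must be noted in CRF for all study participants". The timing is each visit.
- **Leavers.** Section 7.5.1: "The reason why a patient discontinues treatment or study must be documented and these patients must be followed up". What the follow-up covers and how long it lasts are not stated. Section 9.2 adds: "If the patient wants to stop the study completely, the study staff should at least ask the question", and the question that follows is the largest number of standard glasses drunk in one day since the last contact. No visible section names admissions for leavers.
- **Analysis set.** Section 9.2: "The safety assessment will be based on the ITT population". That population is defined as "all randomized patients contributing efficacy data from at least one baseline visit (ITT"), so attending visit 1 is in effect enough.
- **Summary.** No table for hospitalisation is specified. The general rule in section 9.1.1 is "Categorical data will be presented with number (n) and percentage".
- **Missing data and follow-up.** The imputation rules in section 9.2 are written for efficacy and alcohol intake. Section 7.5.1 says "The loss will be reported", and section 7.2.2 says of treatment: "The proportion of patients who remain in treatment will be compared between the patient groups over time". Observed follow-up time for safety is not mentioned.

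**The concern.** Alcohol-related hospitalisation is the one clinical safety item asked about at every visit in both arms; section 7.3.13 asks about device incidents in the TripleA arm only. The item looks back to the previous visit, so a skipped visit is covered at the next one attended. A patient who never returns has no next visit. Admissions between the last visit and exit are not asked about, and admissions after exit are not observed, yet the patient still counts in the ITT denominator.

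A plain n (%) then measures admissions seen during contact, not 12-month admissions. Section 9.2 expects about 20% loss and describes drop-out in alcohol studies as large. Section 7.8.11 hypothesises that more TripleA patients complete aftercare. If study contact followed that pattern, TripleA patients would be observed longer and could show more admissions for that reason alone. Retention in treatment is no substitute for observed time, because section 9.2 foresees patients who stop treatment and stay in the study.

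**Working it through.** **The plan's own figure.** For 30% v 60%, two-sided 5%, 80% power, pooled variance:

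n = [1.960·√(2·0.45·0.55) + 0.842·√(0.30·0.70 + 0.60·0.40)]² / 0.30² ≈ 42 per arm.

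42/0.80 = 52.5, so 53 per arm and 106 in total. Section 9.2 reproduces.

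**Inputs from the plan.** 53 per arm; 20% loss; visits at months 0, 1, 2, 3, 6 and 12.

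**Assumptions, since the plan gives no admission rate.** 12-month admission risk r of 10%, 20% or 30%, equal in both arms and in leavers; exit time uniform over the year; without an exit question, observation ends at the last visit attended.

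**Formulas.** The hazard is kλ in months 0–3 and λ afterwards, with λ = −ln(1−r)/(3k+9); k = 1 is constant and k = 3 is early-weighted. F(t) is the cumulative risk by month t. Uniform exit gives last-visit weights of 1/12, 1/12, 1/12, 3/12 and 6/12 at months 0, 1, 2, 3 and 6.

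- S = weighted mean of F over last visits (leavers seen to the last visit)
- M = mean of F over 0–12 months (leavers seen to exit)
- n (%) without the exit question = (1−d)·r + d·S, where d is the loss
- n (%) with it, all leavers reached = (1−d)·r + d·M

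**Worked case, r = 20%, k = 1, d = 0.20.** λ = 0.2231/12 = 0.0186. F(1), F(2), F(3), F(6) = 0.0184, 0.0365, 0.0543, 0.1056. S = (0 + 0.0184 + 0.0365)/12 + 0.25·0.0543 + 0.5·0.1056 = 0.0709. M = 1 − 0.20/0.2231 = 0.1037.

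- Without: 0.80·0.20 + 0.20·0.0709 = 17.4%.
- With: 0.16 + 0.20·0.1037 = 18.1%.
- Share of shortfall recovered: (18.07 − 17.42)/(20 − 17.42) ≈ 25%.
- Patients recovered per arm: 53·0.20·(0.1037 − 0.0709) = 0.35.

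| Risk | Hazard | S | M | n (%) shown | With exit question | Patients recovered per arm |
|---|---|---|---|---|---|---|
| 10% | constant | 0.034 | 0.051 | 8.7% | 9.0% | 0.18 |
| 20% | constant | 0.071 | 0.104 | 17.4% | 18.1% | 0.35 |
| 30% | constant | 0.110 | 0.159 | 26.2% | 27.2% | 0.52 |
| 10% | early | 0.051 | 0.063 | 9.0% | 9.3% | 0.13 |
| 20% | early | 0.105 | 0.129 | 18.1% | 18.6% | 0.26 |
| 30% | early | 0.161 | 0.196 | 27.2% | 27.9% | 0.38 |

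The shortfall is about 13% in relative terms with a constant hazard and 9 to 10% with the early one. The share of leavers' pre-exit admissions missed, 1 − S/M, is 31 to 33% (constant) or 18 to 19% (early). In both cases the exit question recovers about a quarter of the total shortfall; the rest lies after exit.

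**Less favourable cases at r = 20%, constant hazard.** If every leaver goes straight after visit 1, the table shows 0.80·0.20 = 16.0%. If leavers have twice the hazard, a true 23.2% shows as 18.7%.

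**Tilt between arms, equal true risk.**

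| Loss | Ratio, constant | Ratio, early |
|---|---|---|
| 15% v 25% | 1.08 | 1.05 to 1.06 |
| 10% v 30% | 1.16 | 1.11 to 1.12 |

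At 10% v 30%, r = 20% and constant hazard, the figures are 18.7% v 16.1%, or 53·(0.1871 − 0.1613) = 1.4 patients. The largest gap, at r = 30%, is 2.0 patients. The 95% half-width for a difference, 1.96·√(2r(1−r)/53), is 11.4, 15.2 and 17.4 points for the three risks.

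**Observed time at 20% loss.** The mean last visit for leavers is month 4.0, so patient-years per arm are 53·(0.8·12 + 0.2·4)/12 = 45.9 instead of 53. With the exit question the mean exit is month 6, giving 47.7.

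**The case against.** **The criticised table is not in the plan.** This stands: n (%) is inferred, hospitalisation is not a listed endpoint, and no between-arm test is planned. A reader might infer that the plan counts leavers as free of admissions; no such rule exists. The understatement depends on the general rule being applied and the result being read as a 12-month risk.

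**Existing text may already capture these admissions.** Leavers must be followed up, a contact person is collected at inclusion, and the exit question is a stated minimum. Section 17.1.1 defines adverse events regardless of device relation, and section 17.5 asks for some non-device events to be reported. The monitoring and data management plans are separate and not visible. All this permits an admission question, but none of the visible text secures one. The model, which assumes nothing is learned after the last visit, is therefore a reading of the minimum.

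**Serious-event reporting would catch them.** A reader might infer that every admission is a serious adverse event. Section 17.1.5 requires a serious deterioration in health, and its second note excludes planned stays without one. Section 5.6 names hospital detoxification as a risk-reduction step, so pooling it with harmful admissions would blur the table. This objection is right, and the fix separates the two.

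**Admissions could be retrieved later.** Samples are ordered through a medical record system, so retrieval is possible. Whether staff may consult records after withdrawal is not stated either way.

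**Kaplan-Meier looks unbiased by construction.** This also stands. Its simulated means (19.9 to 20.3% at 20% risk) show no tilt because leavers were given the same hazard. It is also less precise: SD 6.0 v 5.2 points at 20% risk, 20% loss and constant hazard. It is an optional extra.

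**Conclusion.** The point holds as a cheap improvement. Followed to the letter, the plan does not ask about a leaver's admissions between last visit and exit, and nothing planned shows how long each arm was observed for this item. At 20% loss, a plain n (%) would be roughly 9 to 13% too low in relative terms. That size rests on assumed admission risks, uniform exit and leavers having the same risk as stayers; the documents fix none of these.

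A reader might go further and infer a safety comparison biased for or against TripleA. The documents do not support that. Loss by arm is not given, so the direction is unknown. Under fairly extreme differential loss the tilt is at most about 2 patients, well inside sampling error. Sample size and the primary endpoint are untouched.

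**What to change.** 1. **At exit.** At the closing contact already planned in section 9.2, also ask: *Have you been admitted to hospital because of alcohol since your last visit?* There and at visits, record the admission date and whether it was a planned detoxification.
2. **In the analysis text.** After the safety sentence in section 9.2, add: *Alcohol-related hospitalisation is reported by arm as n (%) of the ITT population, with planned detoxification shown separately, together with observed patient-years and the number of patients with no post-baseline safety contact. These summaries are descriptive.* A Kaplan-Meier 12-month estimate by arm, censored at the last contact at which admission was asked about, may be added.

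Both parts are needed, because the question alone leaves about three quarters of the shortfall.

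**Cost.** One question, two CRF fields, one table, and a re-versioned protocol under section 11. Leavers who cannot be reached are still missed, and bias remains if leavers' later admission risk differs.

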9.3. Interim analysis

In order to support the system patent for TripleA, an interim analysis will be made of the following data insofar as they are available before 4 May 2016:

- The proportion of patients who remain in treatment / aftercare in each study arm.
- Proportion of patients who have relapsed in each study arm.
- The app contains questions about daily mood. Modeling will be done on the relationship between daily mood and recurrence rate.

The results will only be summarized in a report that must be attached to a patent application. Data will not be available more than for the limited group performing the analysis. The results will not be available to those who work practically with the study.

10. Data management

Procedures for data management are described in a separate data management plan.

11. Changes to the study protocol

Changes to the study protocol must be decided by a representative of Kontigo Care AB and documented in writing. An updated version of the Protocol, with a new version number and date, shall be distributed to all interested parties. If the patient information is affected by the change, a new version of the patient information must also be produced. Depending on what the change is, it can be decided that the new version will be distributed to already recruited study participants, and / or that it will be used in connection with the consent process for new study participants.

Kontigo Care decides whether the change in the study protocol and / or the patient information is of a material nature and due to this needs to be approved by the ethics review board. The responsible researcher then needs to submit an amendment application to the Ethics Review Board and await approval before the amendment can be implemented.

12. Deviations from the study protocol

The examiner may not deviate from the study protocol, except in emergency situations where deviations from the protocol may be made without the approval of the sponsor or the ethics review board, if this is necessary to protect human rights, safety and well-being. Such deviations must be documented and reported to the sponsor and the ethics review board as soon as possible.

Deviations / changes that affect the subjects' safety, rights and well-being, or the scientific integrity of the study must be submitted to the Ethics Review Board before they are implemented, except for the emergencies mentioned above.

Deviations from the study protocol must be reported to and documented by the project manager. The project manager discusses with the sponsor each deviation in order to reach an agreement on what measures are appropriate to take. When the study is analyzed and reported, this must include any deviations from the study protocol.

13. Responsibility for the test products

Access to the test products must be limited and the test products may only be used within the clinical study and in accordance with the study protocol.

The sponsor must keep documentation of the physical location of all test products from the time they are sent to the test site until they are returned or destroyed.

The principal examiner or a delegated staff member shall maintain a distribution log of the receipt, use, return and destruction of the test products, which shall include:

- date of receipt,
- identification of each test product (batch number / serial number or unique code),
- expiry date, if applicable;
- date of use,
- subject ID,
- date when the test product was returned / removed from the subject, if applicable,
- date of return of unused, expired or malfunctioning test products, if applicable.

14. Compliance with laws, guidelines and standards

This clinical study shall be conducted in accordance with the ethical principles that originate in the Declaration of Helsinki (Declaration of Helsinki, 2013) in accordance with the international standard ISO 14155: 2011 and European and Swedish legislation.

The clinical study shall not begin until approval / positive opinion has been obtained from the ethics review board.

If the Ethics Review Board sets any additional requirements in its opinions, these will be complied with.

15. Insurance

The study participants are covered by the care provider's patient injury insurance with Patientförsäkringen LÖF (County Council's Mutual Insurance Company).

16. Informed consent

Patients are informed before the start of the study both orally and in writing by study staff at the reception. It is emphasized that participation is voluntary and that the subject can withdraw his or her consent at any time without this affecting the patient's future care and treatment. The patient must have the opportunity to ask questions to the staff and have them answered before taking a position on the participation. If the patient chooses to participate after reading the patient information, the consent form is signed and dated by both the patient and the study staff. The patient must be sober when taking a stand

The patient may keep a copy of the entire patient information, including the consent form.

17. Safety reporting

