7.1. Generally

7.1.1. Type of clinical study

The study is a 12-month open and randomized comparison between the control group receiving conventional therapy only and the intervention group receiving conventional therapy enhanced with TripleA.

The study is open because it is the overall concept TripleA that is to be evaluated, which means that both the patient and the therapist must use the tool. A single-blind design could have been used if the goal had been to study the system's components, e.g. only changed patient behavior due to increased support or how therapists' efforts change with or without the information that TripleA can provide. If you want to study the combination effect, the study cannot be blinded. Many treatments work to achieve sobriety or controlled drinking in the short term, but it is more difficult to maintain the effect over time, as the problems behind drinking do not necessarily disappear because you stop drinking or reduce your drinking. The EMA and the FDA, respectively, recommend 12 or 6-month studies, as the drinking pattern at these times has been shown to be predictive of long-term outcomes.

In the current studies, patients will be followed for 12 months to cover all the holidays of the year and other regularly recurring challenges for those who try to refrain from drinking alcohol. An interim analysis is performed after 6 months to obtain data that can support the system patent for TripleA.

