7.7.5. Expected total time required for the clinical study

The study is expected to start in August 2015 and end in November 2016, ie a total of 16 months. Recruitment of study participants is estimated to last for 4 months and each study participant is followed for 12 months.

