7.8.7. Visit 5 (Follow up after 6 months)

- TLFB - See section 8.3.2 and Appendix C.
- Blood test - See section 8.3.8
- AUDIT - See section 8.3.3 above and Appendix D
- CGI Improvement Scale (Clinical Global Impression Severity Score): See section 8.3.6
- EQ-5D: See Section 8.3.7 and Appendix G
- SADD: See section 8.3.1 and Appendix B
- Note changes in medication and other conventional treatment - See section 8.3.10
- Compliance - See section 8.3.12
- Safety reporting - See section 18
- Check that the patient has had a new TripleA device sent home and returned the old one for calibration

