9.1.2.2. Secondary efficacy endpoints

- i) Change in total amount of alcohol consumed per 4-week period after 6 months from "baseline." An ANOVA model for repeated measurements will be used to compare the groups.
- ii) Change in total amount of alcohol consumed per 4-week period after 12 months from "baseline." An ANOVA model for repeated measurements will be used to compare the groups.
- iii) Proportion of completely sober patients at 12 months A logistic regression model will be used to compare the groups.
- iv) Proportion of completely sober patients at 6 months. A logistic regression model will be used to compare the groups.
- v) Change from baseline in the number of heavy drink days per 4-week period at 6 and 12 months, respectively. An ANOVA model for repeated measurements will be used to compare the groups.
- vi) Change from "baseline" in the number of non-drinking days per 4-week period at 6 and 12 months, respectively. An ANOVA model for repeated measurements will be used to compare the groups. Förändring från "baseline" i antalet standardglas per dryckesdag per 4-veckorsperiod vid 6 och 12 månader, respektive. vii) Time to relapse (ie first alcohol intake). For

patients with the goal of becoming alcohol-free, relapse is defined as the first day after "baseline" where alcohol consumption was found, while relapse for patients with the goal of reducing alcohol consumption is defined as the first day after "baseline" where heavy alcohol consumption is found. Heavy consumption is defined for women as a day with 4 or more glasses, while for men it is defined as a day with 5 or more glasses. The data sources TripleA, TLFB or blood samples are used to detect recurrence. To compare the survival curves, ie. the variable time to recurrence, between the treatment groups a log-rank test will be used.

- vii) CGI improvement. The proportion of respondents at follow-up visits is compared between the groups with a logistic regression model.
- viii) EQ-5D. The groups are compared regarding change from "baseline" with ANOVA model. No significant difference is expected, as quality of life forms are generally not particularly sensitive to change after treatment.
- ix) Participation in treatment. To compare the survival curves, ie. the variable time until the treatment is stopped, between the treatment groups a log-rank test will be used.

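### The interim analysis is described as a six-month analysis but is cut at 4 May 2016, so its crude relapse and retention proportions refer to no defined follow-up time

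*Combined protocol and SAP*

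**What the plan says.** Section 7.1.1 states: "An interim analysis is performed after 6 months to obtain data that can support the system patent for TripleA". It does not say from what point the six months are counted.

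Section 9.3 sets a calendar date instead: "an interim analysis will be made of the following data insofar as they are available before 4 May 2016". Two of its three items compare the arms: "The proportion of patients who remain in treatment / aftercare in each study arm" and "Proportion of patients who have relapsed in each study arm". Neither has a time point, a minimum follow-up or a stated denominator. The results go into a report attached to a patent application and are withheld from those who run the study.

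The timeline is in section 7.7.5: "The study is expected to start in August 2015 and end in November 2016, ie a total of 16 months", and "Recruitment of study participants is estimated to last for 4 months and each study participant is followed for 12 months". The study overview (7.3.14) places visits at months 0, 1, 2, 3, 6 and 12.

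Elsewhere the plan treats both outcomes as times to an event. For relapse, section 9.1.2.2 says: "To compare the survival curves, ie. the variable time to recurrence, between the treatment groups a log-rank test will be used". The same section plans a log-rank test for time to stopping treatment. Section 9.1.1 separately plans an evaluation of the 6-month data.

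**The concern.** A proportion of patients who have relapsed, or who are still in treatment, has a meaning only if it is known how long they were observed. A fixed calendar date after staggered entry gives each patient a different length of follow-up. Some will not have reached the six months that section 7.1.1 implies.

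The visit schedule makes this worse, because nothing is planned between month 3 and month 6. A patient just short of month 6 contributes visit data to month 3 only. In the TripleA arm, breath tests are scheduled daily (7.3.12), and section 9.1.2.2 accepts them as a source for detecting relapse. For relapse, the two arms can therefore be observed for different lengths of time at the same cut.

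At stake is the meaning of two figures that leave the trial as evidence in a patent application. They would be neither six-month figures nor figures at any other stated time, and they need not match the six-month evaluation in 9.1.1.

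**Working it through.** **1. The plan's own timeline.** 4 months of recruitment + 12 months of follow-up = 16 months. In calendar months this is 1 August 2015 to 30 November 2016, as 7.7.5 states. The last patient must enter by 30 November 2015. The recruitment window is 31 + 30 + 31 + 30 = 122 days. The 106 patients come from 7.7.7; it reproduces from 9.2 as 42/0.8 = 52.5, rounded up to 53 per arm, times 2.

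**2. Who is short of month 6.** A patient enrolled on 4 November 2015 reaches month 6 on 4 May 2016, the cut-off itself. Those enrolled from 5 to 30 November (26 days) reach it later. Counting 4 November as well gives 27 days, because 9.3 says before the date.

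- Even accrual (assumption): 26/122 = 21.3%, and 0.213 × 106 ≈ 23 patients. With 27 days: 27/122 = 22.1%.
- Later start in August, same end of recruitment, even accrual: from 15 August, 26/108 = 24%; from 31 August, 26/92 = 28%.
- Uneven accrual (assumption), with cumulative share u^k at fraction u of the window and u = 95/122 by 3 November; share short of month 6 = 1 − u^k:

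| Accrual | k | Share short of month 6 |
|---|---|---|
| Front-loaded | 0.5 | 12% |
| Slightly front-loaded | 0.8 | 18% |
| Even | 1 | 22% |
| Back-loaded | 1.5 | 31% |
| Strongly back-loaded | 2 | 39% |

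The documents give no accrual pattern.

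**3. Time since enrolment at the cut.** From 30 November 2015 to 4 May 2016 is 156 days; from 1 August 2015 it is 277 days. Divided by 30.44 days per month, the range is 5.1 to 9.1 months.

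**4. What is actually observed.** No patient can have reached month 12, so the last scheduled visit before the cut is month 6 or month 3.

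- Short of month 6: visit data end at month 3, while TripleA tests can run to the cut. The gap is 5.1 − 3 = 2.1 months for the last patient enrolled and 181/30.44 − 3 = 2.9 months for one enrolled on 5 November.
- Past month 6: visit data end at month 6, and TripleA tests can run up to 9.1 − 6 = 3.1 months further.

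These gaps apply to relapse. Retention is documented at study visits in both arms (7.2.2).

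**5. Month 3.** A patient enrolled on 30 November 2015 reaches month 3 on 29 February 2016, before the cut. On the plan, every patient can contribute to a month-3 estimate.

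**The case against.** The strongest case on the other side is that this is a non-decisional snapshot. Section 9.3 attaches no stopping rule, adaptation or hypothesis test. It openly accepts incomplete data, and the six-month evaluation and log-rank analyses are planned elsewhere. Randomisation is 1:1 in permuted blocks (7.1.3.1), so calendar exposure should be similar in the two arms. All of this stands, and it keeps the point minor. It does not give the two proportions a time point, and balanced calendar time does not balance observation when one arm is tested daily and the other is seen at visits.

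Four stronger readings are tempting and should be resisted.

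- A reader might infer that relapse is understated and retention overstated. Section 9.3 gives no denominator, so it does not say that patients without month-6 data count as event-free. TripleA results beyond month 6 could also push the relapse figure up in one arm. The direction is not settled.
- A reader might treat a fifth as a minimum. It depends on even accrual; front-loaded accrual gives less. Scenarios that enrol into December 2015 do not fit the stated end in November 2016.
- A reader might convert the missing patients into lost power. The 80% power in 9.2 belongs to the 12-month primary endpoint, which is not among the interim items.
- A reader might model a relapse curve from the 30% in 9.2. That figure is the proportion without heavy drinking days in one 4-week window, not relapse-free survival. The documents give no relapse-free rate.

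**Conclusion.** The point holds as a minor one. Sections 7.1.1 and 9.3 do not agree on the planned timeline, and the two interim proportions refer to no defined follow-up time. About a fifth of patients (roughly 23 of 106) would be short of month 6 if accrual is even from 1 August to 30 November 2015, with about 12% to 39% under the other patterns tried. Time since enrolment spans about 5 to 9 months, but that is calendar time: visit data stop at month 3 or month 6.

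The unequal observation of relapse between arms assumes that 9.3 uses the sources in 9.1.2.2 (TripleA, TLFB or blood samples). Section 9.3 does not say so, and 7.2.2 defines relapse by the patient's own information. The lack of a time point does not depend on this.

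The primary analysis at 12 months, its error rate and the sample size are unaffected.

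**What to change.** - **Section 9.3:** replace the two crude proportions by Kaplan-Meier estimates by arm, at month 3 and month 6 from randomisation. Censor both arms at the last completed visit before the cut, and print the number at risk at each time. This matches the time-to-event treatment of both outcomes in 9.1.2.2.
- **Section 7.1.1:** replace the six-month description by the calendar cut-off, and say that not all patients will have reached month 6. Do not write in a fixed expected percentage, because it would rest on an accrual pattern that the plan does not give.

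The cost is a few sentences and a few lines of code. The month-6 estimate will have a wider interval, and TripleA data after the last visit are not used in this comparison. Common censoring removes the difference in length of observation. It does not remove the difference in detection that section 7.8.11 already acknowledges. Nor does it fill the gap between months 3 and 6: with TLFB limited to the 4 weeks before each visit (7.3.2), about (183 − 91) − 28 = 64 days there have no TLFB record. The month-3 estimate is therefore the cleaner of the two.
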